12.3 Criteria to resume dosing

Subjects may resume treatment with nivolumab when the drug-related AE(s) resolve(s) to Grade ≤ 1 or baseline, with the following exceptions:

- Subjects may resume treatment in the presence of Grade 2 fatigue.
- Subjects who have not experienced a Grade 3 drug-related skin AE may resume treatment in the presence of Grade 2 skin toxicity.
- Subjects with baseline Grade 1 AST/ALT or total bilirubin who require dose delays for reasons other than a 2-grade shift in AST/ALT or total bilirubin may resume treatment in the presence of Grade 2 AST/ALT OR total bilirubin.
- Drug-related pulmonary toxicity, diarrhea, or colitis must have resolved to baseline before treatment is resumed. Subjects with persistent Grade 1 pneumonitis after completion of a steroid taper over at least 1 month may be eligible for retreatment if discussed with and approved by IFCT.
- Drug-related endocrinopathies adequately controlled with only physiologic hormone replacement may resume treatment after consultation with IFCT.

- Subjects who delay study treatment due to any Grade ≥ 3 amylase or lipase abnormality that is not associated with symptoms or clinical manifestations of pancreatitis, may resume nivolumab when the amylase or lipase abnormality has resolved to Grade < 3 . IFCT should be consulted prior to resuming nivolumab in such subjects.
- Dose delay of nivolumab which results in treatment interruption of > 6 weeks requires treatment discontinuation.

12.4 Discontinuation of treatment

Treatment with nivolumab should be permanently discontinued for any of the following:

- Any Grade ≥ 3 drug-related pneumonitis or interstitial lung disease
- Grade 4 colitis or diarrhea
- Grade ≥ 3 elevation in AST, ALT or total bilirubin
- Grade 4 creatinine elevation
- Grade 4 rash, grade 4 pruritus
- Grade 2 or 3 immune-related adverse reactions that persist despite treatment modifications or for inability to reduce corticosteroid dose to 10 mg prednisone or equivalent per day.
- Dosing delays lasting > 6 weeks from the previous dose that occur for non-drug-related reasons may be allowed if approved by IFCT. Prior to re-initiating treatment in a subject with a dosing delay lasting > 6 weeks, IFCT must be consulted. Tumor assessments should continue as per protocol even if dosing is delayed. Periodic study visits to assess safety and laboratory studies should also continue or more frequently if clinically indicated during such dosing delays.
- Any adverse event, laboratory abnormality, or intercurrent illness which, in the judgment of the Investigator, presents a substantial clinical risk to the subject with continued nivolumab dosing.

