4 ELIGIBILITY

4.1 Inclusion Criteria

1. Age ≥ 18 years old
2. HIV1 or HIV2, regardless of CD4 cell count
3. HIV Viral load <200 copies/mL
4. Proven histologically and/or cytologically, stage IIIB-IV or metastatic relapse post-surgery non-small cell lung cancer (NSCLC)
5. Disease recurrence or progression during/after at least one prior platinum doublet-based chemotherapy regimen for advanced or metastatic disease
6. Measurable disease by Computed tomography (CT)/Magnetic resonance imaging (MRI) per RECIST 1.1 criteria
7. Performance status (PS) 0, 1 or 2
8. Written informed consent
9. Patients must have adequate organ function: creatinine clearance > 40 mL/min (Cockcroft, MDRD or CKD-Epi formula or 24h Urine Calculate creatinine clearance from a 24h urine collection), neutrophiles count > 1500/mm³; platelets > 100 000/mm³ ; hemoglobine > 9 g/dL; hepatic enzymes < 3N with total bilirubin ≤ 1.5 × ULN (upper limit of normal) except subjects with documented Gilbert's syndrome (≤ 5 × ULN) or liver metastasis, who must have a baseline total bilirubin ≤ 3.0 mg/dL
10. Patients must receive appropriate care and treatment for HIV infection including ART when clinically indicated and subjects should be under the care of a physician experienced in HIV management. In case of recent introduction of cART and CD4 levels <50 cells/ml, inclusion will be possible provided subjects had at least 4 weeks of

treatment prior to inclusion, to avoid clinical type IRIS (immune inflammatory syndrome reconstitution). All antiretroviral treatments are allowed.

11. Females of childbearing potential who are sexually active with a nonsterilized male partner must use a highly effective method of contraception for 28 days prior to the first dose of investigational product, and must agree to continue using such precautions for 6 months after the final dose of investigational product; cessation of contraception after this point should be discussed with the referent physician. Periodic abstinence, the rhythm method, and the withdrawal method are not acceptable methods of contraception. They must also refrain from egg cell donation for 6 months after the final dose of investigational product. Men receiving nivolumab and who are sexually active with women of childbearing potential will be instructed to adhere to contraception (appendix I) for a period of 31 weeks after the last dose of nivolumab.

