Important medical events that may not be immediately life-threatening or result in death or hospitalization but may jeopardize the patient or may require intervention to prevent one of the other outcomes listed in the definition above should also usually be considered serious. Examples of such events include allergic bronchospasm requiring intensive treatment in an emergency room or at home, blood dyscrasias or convulsions that do not result in inpatient hospitalization, or the development of drug dependency or drug abuse, or suspected transmission of an infectious agent (eg pathogenic or nonpathogenic) via the study drug, or overdose of treatment, or lab test abnormalities clinically significant.

A diagnosis of cancer during the course of a treatment should be considered as medically important. The List of Critical Terms (1998 adaptation of World Health Organization Adverse Reaction Terminology Critical Terms List, provided in the “Instructions for completing the ‘Serious Adverse Event/Expedited Report from a Clinical Trial’ form”) should be used as guidance for adverse events that may be considered serious because they are medically important.

⁵ Wherever possible, timely confirmation of initial liver-related laboratory abnormalities should occur prior to the reporting of a potential DILI event. All occurrences of potential DILIs, meeting the defined criteria, must be reported as SAEs. Potential DILI is defined as:

1) ALT or AST elevation >3 times upper limit of normal (ULN)

AND

2) Total bilirubin >2 times ULN, without initial findings of cholestasis (elevated serum alkaline phosphatase)

AND

3) No other immediately apparent possible causes of AST/ALT elevation and hyperbilirubinemia, including, but not limited to, viral hepatitis, pre-existing chronic or acute liver disease, or the administration of other drug(s) known to be hepatotoxic.

A hepatic AE management algorithm has been established according to nivolumab IB for appropriate management of DILI cases (cf; appendix II).

The following hospitalizations are not considered SAEs:

- A visit to the emergency room or other hospital department < 24 hours, that does not result in admission (unless considered an important medical or life-threatening event)
- Elective surgery, planned prior to signing consent
- Admissions as per protocol for a planned medical/surgical procedure
- Routine health assessment requiring admission for baseline/trending of health status (eg, routine colonoscopy)

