12.2 Dose Delay

Nivolumab administration should be delayed for the following:

- Grade 2 pneumonitis
- Grade 2 or 3 diarrhea or colitis
- Grade 2 elevation in AST, ALT or total bilirubin
- Grade 2 or 3 creatinine elevation
- Symptomatic endocrinopathies (including hypothyroidism, hyperthyroidism, hypophysitis, adrenal insufficiency and diabetes)
- Grade 3 rash
- Any AE, laboratory abnormality or intercurrent illness which in the judgment of the investigator, warrants delaying the dose of study medication.

Subjects who require delay of nivolumab should be re-evaluated weekly or more frequently if clinically indicated and resume nivolumab dosing when re-treatment criteria are met.

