12.5 Management Algorithms for Immuno-Oncology Agents

Immuno-oncology (I-O) agents are associated with AEs that can differ in severity and duration than AEs caused by other therapeutic classes. Nivolumab is considered immuno-oncology agents in this protocol. Early recognition and management of AEs associated with immuno-oncology agents may mitigate severe toxicity. Management Algorithms have been developed to assist investigators in assessing and managing the following groups of AEs:

- Gastrointestinal

- Renal
- Pulmonary
- Hepatic
- Endocrinopathy
- Skin
- Neurological

The above algorithms are found in Appendix II.

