APPENDIX II

Renal Adverse Event Management Algorithm

[figure not shown]
Rule out non-inflammatory causes. If non-inflammatory cause, treat accordingly and continue I-O therapy

Patients on IV steroids may be switched to an equivalent dose of oral corticosteroids (e.g. prednisone) at start of tapering or earlier, once sustained clinical improvement is observed. Lower bioavailability of oral corticosteroids should be taken into account when switching to the equivalent dose of oral corticosteroids.

GI Adverse Event Management Algorithm

[figure not shown]
Rule out non-inflammatory causes. If non-inflammatory cause is identified, treat accordingly and continue I-O therapy. Opiates/narcotics may mask symptoms of perforation. Infliximab should not be used in cases of perforation or sepsis.

Patients on IV steroids may be switched to an equivalent dose of oral corticosteroids (e.g. prednisone) at start of tapering or earlier, once sustained clinical improvement is observed. Lower bioavailability of oral corticosteroids should be taken into account when switching to the equivalent dose of oral corticosteroids.

Pulmonary Adverse Event Management Algorithm

[figure not shown]
Rule out non-inflammatory causes. If non-inflammatory cause, treat accordingly and continue I-O therapy. Evaluate with imaging and pulmonary consultation.

Patients on IV steroids may be switched to an equivalent dose of oral corticosteroids (e.g. prednisone) at start of tapering or earlier, once sustained clinical improvement is observed. Lower bioavailability of oral corticosteroids should be taken into account when switching to the equivalent dose of oral corticosteroids.

Hepatic Adverse Event Management Algorithm

Rule out non-inflammatory causes. If non-inflammatory cause, treat accordingly and continue I-O therapy. Consider imaging for obstruction.

[figure not shown]
Patients on IV steroids may be switched to an equivalent dose of oral corticosteroids (e.g. prednisone) at start of tapering or earlier, once sustained clinical improvement is observed. Lower bioavailability of oral corticosteroids should be taken into account when switching to the equivalent dose of oral corticosteroids.

*I-O therapy may be delayed rather than discontinued if AST/ALT ≤ 8 x ULN or T.bili ≤ 5 x ULN.

**The recommended starting dose for grade 4 hepatitis is 2 mg/kg/day methylprednisolone IV.

Endocrinopathy Management Algorithm

[figure not shown]

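### Section 12.4 stops nivolumab for good at any Grade 3 or higher liver test, the Appendix II hepatic footnote allows a delay instead, and nothing says which prevails

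*Protocol*

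**What the plan says.** Four places in the protocol bear on a raised liver test under treatment.

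- **Section 12.2** lists the reasons to delay a dose. The hepatic entry is "Grade 2 elevation in AST, ALT or total bilirubin". Grade 3 is not in that entry, although the diarrhoea/colitis and creatinine entries in the same list do include Grade 3.
- **Section 12.4** lists the reasons for which treatment should be stopped permanently. The hepatic entry is "Grade ≥ 3 elevation in AST, ALT or total bilirubin", with no exception and no limit in multiples of the upper limit of normal (ULN).
- **Appendix II**, under the hepatic algorithm, carries an asterisked footnote: "I-O therapy may be delayed rather than discontinued if AST/ALT ≤ 8 x ULN or T.bili ≤ 5 x ULN".
- **Sections 11.2 and 12.5** point to the algorithms. Section 11.2 says: "A hepatic AE management algorithm has been established according to nivolumab IB for appropriate management of DILI cases". Section 12.5 says: "Management Algorithms have been developed to assist investigators in assessing and managing the following groups of AEs". Neither says how an algorithm relates to the lists in sections 12.2 and 12.4.

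For patients whose dose was delayed, section 12.3 generally allows treatment to resume "when the drug-related AE(s) resolve(s) to Grade ≤ 1 or baseline", and it requires discontinuation if the interruption exceeds 6 weeks.

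**The concern.** A stopping rule for liver toxicity should give one answer for one laboratory result. Here the body text gives a permanent stop and the appendix permits a delay, after which the patient may be treated again under section 12.3. An investigator could do either and cite the protocol.

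The safety of re-exposure is the main stake. Liver abnormalities are foreseeable in this trial: hepatitis B and C co-infection is monitored, and hepatic enzymes up to three times normal are allowed at entry. The second stake is consistency of the data. Thirty patients are planned over twenty centres, so each centre will meet the situation rarely, if at all, and will rely on the written rule. Tolerance is the first secondary endpoint in section 2.2. Counts of discontinuation for toxicity, and exposure, would partly reflect which page a site had read.

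**Working it through.** This is a comparison of texts; the plan has no figure to reproduce.

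**Step 1. What each text directs, by grade.**

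| Liver test result | Section 12.2 | Section 12.4 | Appendix II hepatic footnote |
|---|---|---|---|
| Grade 2 | Delay | Not in the hepatic entry | Adds little: already a delay |
| Grade 3 or higher, within 8 x ULN (AST/ALT) or 5 x ULN (bilirubin) | Not in the hepatic entry | Permanent stop | Delay permitted |
| Grade 3 or higher, above those limits | Not in the hepatic entry | Permanent stop | No exception |

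The conflict is in the second row.

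**Step 2. Is the second row empty?** The footnote is an exception to discontinuation, so it has effect only where discontinuation would otherwise follow. For a liver test judged on its grade, section 12.4 sets that point at Grade 3. The row contains values as long as Grade 3 starts below 8 x ULN for AST/ALT, or below 5 x ULN for bilirubin.

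The protocol names CTCAE v4 but prints no cut-offs. Assumption: Grade 3 starts above 5 x ULN for AST/ALT and above 3 x ULN for bilirubin. The disputed ranges are then:

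- AST/ALT: above 5 and up to 8 x ULN
- total bilirubin: above 3 and up to 5 x ULN

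A different Grade 3 start moves the lower end of each range. The conflict remains for any start below 8 and 5 x ULN respectively.

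**Step 3. Does any text settle it?** Sections 11.2, 12.2, 12.3, 12.4, 12.5 and Appendix II were read for a statement of precedence. There is none. Section 12.5 describes the algorithms as an aid, and section 11.2 presents the hepatic one as the appropriate management of drug-induced liver injury. These descriptions pull in different directions, and neither is a ranking.

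**Step 4. Consequence for one patient.** Take AST at 6 x ULN with normal bilirubin, which is Grade 3 under the assumption above. Section 12.4 leads to no further nivolumab. The footnote leads to a delay and, if AST returns to Grade 1 or baseline within the 6-week limit, to further nivolumab.

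**The case against.** The strongest reply is that the two texts differ in status. Section 12.4 is the listed stopping rule, while the algorithms are offered as assistance and the footnote says only that therapy may be delayed. A careful reader could conclude that 12.4 governs and that the algorithm guides work-up and steroid treatment. That is a reasonable reading, but the protocol does not state it. Section 12.4 itself says treatment should be discontinued, which is also not absolute wording.

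A second reply is that the hepatic flow chart is not shown, so the box carrying the asterisk, and any condition in it, cannot be seen. Section 12.4 also stops treatment for immune-related reactions of Grade 2 or 3 that persist, and the footnote might have been meant for those. This limit stands: the link to the Grade 3 entry is an inference. It is a strong one, because the printed footnote gives delay as the alternative to discontinuation and sets limits in ULN multiples without mentioning persistence.

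A reader might also infer three stronger points, which the documents do not support.

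- *That section 12.3 itself prescribes a delay at Grade 3.* Its bullet covers patients with Grade 1 liver tests at baseline "who require dose delays for reasons other than a 2-grade shift in AST/ALT or total bilirubin". This only excludes a 2-grade shift from an exception that allows resumption at Grade 2. It is compatible with 12.4 stopping those patients.
- *That the word 'or' in the footnote removes the AST/ALT ceiling whenever bilirubin is low.* The natural reading is that each analyte has its own limit.
- *That some patients meet the stopping rule on entry.* Inclusion criterion 9 makes a bilirubin allowance, "except subjects with documented Gilbert's syndrome (≤ 5 × ULN) or liver metastasis", but the wording around it is unclear and the argument needs an assumed grade cut-off. Section 11.1 defines adverse events as developing or worsening during observation, so a stable raised bilirubin at entry need not count as an elevation on treatment.

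**Conclusion.** The inconsistency is real and should be corrected. For Grade 3 or higher AST, ALT or total bilirubin within the footnote's limits, section 12.4 and Appendix II give opposite directions, and no text resolves them. The conclusion rests on the printed wording and on Grade 3 starting below 8 x ULN (AST/ALT) or 5 x ULN (bilirubin). It carries the reservation that the flow chart is not visible.

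The size cannot be expressed in patients, because the protocol gives no rate of Grade 3 liver tests. The effect is on patient safety, drug exposure and the consistency of toxicity discontinuations between sites. A reader might go on to infer a bias in the 8-week disease control rate; nothing in the protocol establishes one. The sample size and the decision rule are not affected.

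**What to change.** Choose one rule and write it in one place. The choice is clinical and belongs to the sponsor's clinicians.

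1. **If Grade 3 or higher is to be a permanent stop:** add to section 12.4 *For AST, ALT and total bilirubin, section 12.4 prevails over Appendix II*, and delete the hepatic footnote or mark it as not applicable in this trial. Sections 12.2 and 12.3 can stay as they are.
2. **If the exception is intended:** write it into section 12.4 with a limit for each analyte, add the matching Grade 3 delay to section 12.2, and let resumption follow the existing section 12.3 criterion. Keep the precedence sentence and make the footnote agree with it.

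The first option costs one sentence in 12.4 and one footnote. The second costs one entry each in 12.2 and 12.4, the precedence sentence and the footnote. Neither changes the sample size, visits or endpoints. If the change is classed as substantial, section 15.4 requires an amendment submitted to the ethics committee and the health authority, so the cost includes that submission and notice to the sites.

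### Section 12.4 permanently stops nivolumab for any Grade ≥ 3 liver elevation, Appendix II allows delay or continuation for some of the same values, and nothing says which governs

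*Protocol*

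**What the plan says.** **Section 12.4** opens with "Treatment with nivolumab should be permanently discontinued for any of the following" and includes the bullet "Grade ≥ 3 elevation in AST, ALT or total bilirubin". The bullet does not mention cause, baseline or a multiple of ULN, and does not point to Appendix II. The pneumonitis bullet in the same list is restricted to drug-related events; the liver bullet is not.

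**Section 12.2** delays dosing for Grade 2 elevations of the same three tests.

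**Appendix II, hepatic algorithm**, gives two allowances. On cause: "If non-inflammatory cause, treat accordingly and continue I-O therapy. Consider imaging for obstruction". On level: "I-O therapy may be delayed rather than discontinued if AST/ALT ≤ 8 x ULN or T.bili ≤ 5 x ULN".

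**Status of the algorithms.** Section 12.5 introduces them as an aid: "Management Algorithms have been developed to assist investigators in assessing and managing the following groups of AEs". Section 11.2 gives the hepatic one a firmer role: "A hepatic AE management algorithm has been established according to nivolumab IB for appropriate management of DILI cases".

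**Baseline.** Criterion 9 in section 4.1 limits total bilirubin at entry, "except subjects with documented Gilbert's syndrome (≤ 5 × ULN) or liver metastasis", and adds a cap of 3.0 mg/dL. Section 12.3 lets dosing resume once a drug-related event returns to Grade 1 or less or to baseline, with a specific bullet for "Subjects with baseline Grade 1 AST/ALT or total bilirubin who require dose delays for reasons other than a 2-grade shift".

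**The concern.** A dosing rule should give one answer for one laboratory value. Here a site reading section 12.4 stops nivolumab for good, while a site reading Appendix II may delay it, or continue it if the cause is judged non-inflammatory. The possible harm runs both ways: a patient may lose a second-line or later treatment without need, or be dosed again where the body of the protocol meant a stop.

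Section 3 plans thirty patients in twenty centres, or 30/20 = 1.5 per centre. A site will rarely meet the case twice, so no local practice will settle the question.

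This population makes liver values raised by something other than nivolumab foreseeable. Criterion 9 makes allowance for Gilbert's syndrome and liver metastasis, all antiretrovirals are permitted, and hepatitis B and C co-infection is monitored rather than excluded.

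**Working it through.** The plan states no figure to reproduce. The check sets the texts side by side and then sizes the overlap.

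**Step 1. Does the conflict need outside cut-offs?** No.
- Section 12.2 already delays at Grade 2, and the only liver-grade stop in section 12 is the Grade ≥ 3 bullet in 12.4. A permission to delay in place of discontinuing therefore has effect only at Grade ≥ 3, where 12.4 orders a permanent stop.
- The instruction to continue for a non-inflammatory cause conflicts with 12.4 at every Grade ≥ 3 value.

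**Step 2. How wide is the overlap?** The text at hand prints no CTCAE cut-offs. Let Grade 3 start above b x ULN for bilirubin and above a x ULN for AST/ALT. The overlap is 5 − b and 8 − a, in multiples of ULN.

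| Bilirubin, assumed b | Width 5 − b | AST/ALT, assumed a | Width 8 − a |
|---|---|---|---|
| 2 | 3 | 4 | 4 |
| 3 | 2 | 5 | 3 |
| 4 | 1 | 6 | 2 |
| 5 or more | none | 8 or more | none |

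With b = 3 and a = 5, the bands are bilirubin above 3 to 5 x ULN and AST/ALT above 5 to 8 x ULN. At an assumed bilirubin ULN of 1.0 to 1.2 mg/dL, 3 x ULN is 3.0 to 3.6 mg/dL and 5 x ULN is 5.0 to 6.0 mg/dL.

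**Step 3. Which text governs?** Section 12.5 suggests that the algorithms are advisory; section 11.2 names the hepatic one as the way to manage DILI cases. No sentence sets an order.

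**Step 4. How many patients?** The protocol gives no rate. If a share p of patients ever enters a band (assumed), the expected number is 30p and the chance of at least one is 1 − (1 − p)^30:
- p = 1%: 0.3 patients, 26.0%
- p = 3%: 0.9 patients, 59.9%
- p = 5%: 1.5 patients, 78.5%

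These figures only illustrate scale.

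**Step 5. Gilbert's syndrome.** An eligible patient can meet the 12.4 wording with no drug effect if all three of these hold:
1. Criterion 9 admits Gilbert's up to 5 x ULN, with the 3.0 mg/dL cap applying to liver metastasis only.
2. Grade 3 bilirubin starts above 3 x ULN.
3. A value already present at entry counts as an elevation.

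If the cap also covers Gilbert's, entry bilirubin is at most 3.0/1.2 = 2.5 to 3.0/1.0 = 3.0 x ULN, and the overlap at entry disappears. The conflict over on-treatment values in steps 1 to 3 does not.

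**The case against.** The strongest reply is that 12.4 is a directive in the body of the protocol, whereas the algorithms are offered as help and their footnote is permissive. On that view 12.4 simply governs. A strict liver stop may also be deliberate in a trial that section 1.3 wants run under maximum security and that monitors hepatitis co-infection. This is a fair reading, but the protocol does not state it, and 11.2 points investigators to the hepatic algorithm. If it is what the sponsor means, one sentence would settle it.

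Second, the hepatic flow chart is not shown. It may print thresholds, and the box carrying the footnote cannot be seen. That limits what can be said about the exact bands, but the footnote's wording is enough to establish the conflict.

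Third, a reader might infer that Gilbert's patients are enrolled only to be stopped at once. The documents do not support that. It needs all three conditions in step 5, and section 11.1 defines an adverse event as something that develops or worsens, which favours reading an elevation as a change on treatment. Gilbert's is a secondary, conditional example.

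Fourth, a reader might infer that the protocol has no general baseline-relative rule for liver values. It has one: the opening line of 12.3 allows resumption at baseline. But it governs resumption only and cannot bring back a patient whom 12.4 has permanently stopped.

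**Conclusion.** The contradiction is real and follows from the protocol's own text. For an on-treatment Grade ≥ 3 AST, ALT or bilirubin value, 12.4 says stop permanently and Appendix II may say delay or continue, with no stated precedence. The cause-based conflict needs no assumption about cut-offs. The level-based bands (AST/ALT above 5 to 8 x ULN, bilirubin above 3 to 5 x ULN) rest on assumed Grade 3 limits, and some overlap exists for any limits below 8 and 5 x ULN.

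Few patients are likely to be affected, and the true frequency is unknown. This is a dosing and safety inconsistency that should be corrected. It does not alter the sample size, the decision rule or the error rates.

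**What to change.** **Preferred change, section 12.4.** Make the liver bullet refer to the Appendix II hepatic algorithm and say that it governs within limits:
- At Grade ≥ 3, delay instead of discontinuing only if AST/ALT is ≤ 8 x ULN **and** total bilirubin is ≤ 5 x ULN **and** the potential-DILI criteria of 11.2 are not met. Otherwise discontinue permanently.
- The allowance to continue for a documented non-inflammatory cause is subject to the same ceilings.

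The footnote's *or* should not be carried over: read literally, AST at 15 x ULN with normal bilirubin would qualify for delay. The DILI condition is needed as well. AST at 7 x and bilirubin at 4 x ULN pass both ceilings, yet exceed both laboratory limits for potential DILI in 11.2 (3 x and 2 x ULN).

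**Gilbert's syndrome, sections 12.2 and 12.4.** For documented Gilbert's, apply the bilirubin rules to a rise over the recorded baseline, and add total bilirubin > 5 x ULN as a new explicit absolute stop.

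**Alternative.** If the stricter rule is intended, state that 12.4 prevails over Appendix II and keep only the Gilbert's baseline exception.

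**Cost.** A few sentences and no new tests, because section 8.1 already measures bilirubin and AST/ALT before each infusion. Criterion 9 and the DILI reporting in 11.2 stay as they are. The preferred change makes the liver stop slightly less conservative for a few patients. Weekly re-evaluation under 12.2, the ceilings above and the investigator-judgment stop in 12.4 remain as safeguards. The 6-week limit on delay in 12.3 is weaker protection, since 12.4 lets the sponsor approve longer delays for non-drug-related reasons.
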